#### **11.3.6 Exploratory Analysis of Efficacy**

The following will be tabulated for the full analyses set.

The number and percentage of subjects with ‘substantial resolution’ of clinical signs for the target lesion will be tabulated by visit and treatment group.

The general change in target lesion will be tabulated by treatment group and visit. The clinical signs for the target lesion from baseline to all subsequent visits will be tabulated by treatment group, as both the number and percentage of subjects in each category (markedly improved, moderately improved, slightly improved, unchanged and aggravated). Further, the number and percentage of subjects with a change of ‘moderately improved’ or better will be tabulated by treatment group and visit.

The change in total sign score for the target lesion from baseline to Visits 2 and 3 (end of Weeks 1 and 2) by treatment will be summarised as mean, SD, median, minimum and maximum values.

The change in score for the severity of each clinical sign for the target lesion from baseline to each subsequent visit by treatment will be summarised as mean, SD, median, minimum and maximum values. In addition, the estimated difference between the treatment groups (LEO 90100 foam group – Dovobet® ointment group) in the mean change from baseline to Visit 4 (end of Week 4) will be calculated for each clinical sign with 95% confidence interval.

### **11.3.7 Exploratory Analysis of Subject Assessments**

The number and percentage of subjects in each category for ‘time spent for application’ (less time, slightly less time, unchanged, slightly more time, more time) and ‘ease of application’ (very easy, easy, difficult, very difficult) will be tabulated at Visit 4 (end of Week 4) by treatment group.

In addition, a difference between the two treatment groups will be calculated for each subject assessment with odds ratio and 95% confidence interval.

### **11.3.8 Analysis of Safety**

The analysis of safety will be based on the safety analysis set.

#### **11.3.8.1 Adverse Events**

AEs will be coded during the course of the trial according to MedDRA. AEs will be presented by preferred terms and primary system organ class.

Only treatment emergent AEs will be tabulated but all AEs recorded during the course of the trial will be included in the subject data listings. An event will be considered emergent with the trial treatment if started after the first application of IMP or if started before the first

application of IMP and worsened in severity thereafter. In each of the tabulations, AEs are defined by MedDRA preferred terms within primary system organ class.

An overall summary of AEs and number (percentage) of subjects with any AEs, SAEs, premature discontinuations from the trial due to AEs, treatment related AEs and AEs stratified by severity will be presented.

The number of AEs and number (percentage) of subjects for each type of AE will be tabulated by treatment group. A similar tabulation will be made for AEs stratified by severity.

The causal relationship to trial medication for each type of AEs will be tabulated by treatment group. Where there are several recordings of causal relationship to the IMP for a given type of AE for a subject, causal relationship will be taken as the most-related recording from the last report of that AE, since that is when the (sub)investigator will be in possession of most information and so best able to judge causal relationship.

Related AEs are defined as AEs for which the (sub)investigator has not described the causal relationship to IMP as 'not related'. The number of subjects experiencing each type of related AE will be tabulated regardless of the number of times each related AE is reported by each subject.

Cutaneous AEs will be tabulated, similarly stratified as 'lesional/perilesional' or 'distant'.

SAEs will be evaluated separately and a narrative for each will be given.

AEs leading to withdrawal from trial or discontinuation of IMP will be listed.

### **11.3.8.2 Clinical Laboratory Evaluation**

The observed values and change from baseline in each of the haematology and chemistry laboratory parameters will be summarised as mean, geometric mean, coefficient of variation, SD, median, minimum and maximum values.

The haematology and chemistry laboratory parameters will also be classified as 'low', 'normal' or 'high', depending on whether the value is below, within or above the reference range, respectively. Urine glucose and protein will be classified as 'absent' or 'present'. Shift tables will be produced showing the categories at Visit 1 (baseline) against those at Visit 4 (end of Week 4).

Laboratory parameters outside the reference range will be indicated in the subject data listings.

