### Urine, semi-quantitatively

Urine Glucose, urine protein

The central laboratory will provide the material and instructions necessary for the collection and transport of the samples, analyse the samples.

If any laboratory results are clinically abnormal, the (sub)investigator should follow-up the subject as clinically appropriate. Any laboratory abnormality assessed as clinically significant by the (sub)investigator must be recorded as an AE in eCRF.

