#### Betamethasone dipropionate

AEs found in connection with systemic corticosteroid treatment, such as adrenocortical suppression or impact on the metabolic control of diabetes mellitus, may occur also during topical corticosteroid treatment due to systemic absorption.

There may be a risk of generalised pustular psoriasis or of rebound effects when discontinuing treatment. Medical supervision should therefore continue in the post-treatment period.

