### 4. Adverse drug reactions

In clinical studies conducted in Japan before approval of Ointment and before approval of Gel, 17 adverse drug reactions were reported in 17 of the 445 treated patients (3.8%).

Those adverse drug reactions were folliculitis in 5 patients, anaemia and glucose urine present in 2 patients each, and leukocytosis, oedema peripheral, hepatic function abnormal, herpes simplex, rash pustular, contusion, psoriasis aggravated and skin depigmentation in 1 patient each.

- (1) Clinically significant adverse drug reactions
- 1) Hypercalcemia (information from Package Insert of calcipotriol, frequency unknown): Hypercalcemia and clinical symptoms that are considered to be due to hypercalcemia (malaise, feelings of weakness, anorexia, vomiting, abdominal pain and muscle weakness, etc.) may appear. If any abnormalities are noted, use of this medication should be discontinued, and biochemical tests including serum calcium and urine calcium should be conducted. If necessary, actions such as intravenous fluids should be taken.

2) Acute kidney injury (information from Package Insert of calcipotriol, frequency unknown): Acute kidney injury accompanied by serum calcium increased may appear. If any abnormalities such as serum creatinine increased and BUN increased are noted, use of this medication should be discontinued, and an appropriate action should be taken.

(2) Other adverse drug reactions

If the following adverse drug reactions are observed, appropriate measures should be taken.

	≥ 1%	< 1%	Unknown*
Hypersensitivity note1			Erythema/redness,
Skin note2		Psoriasis aggravated	Itch, pruritus, burning sensation, pricking skin feeling, skin irritation, dermatitis, Ichthyosis-like dermal changes, skin dryness, skin erosion, contact dermatitis, exfoliation, eruption, swelling
Skin infection note3	Folliculitis		Bacterial infection (infectious impetigo, furuncle, etc.), dermatomycosis (candidiasis, tinea, etc.), viral infection
Other skin symptoms note4		Rash pustular, Skin depigmentation	Skin pigmentation, pustular psoriasis, acneform eruption, rosacea-like dermatitis, steroid skin (skin atrophy, telangiectasis and purpura), hypertrichosis,
Hepatic		Hepatic function abnormal	Increased AST(GOT), increased ALT(GPT) increased $\gamma$ -GTP, increased LDH, increased ALP, increased total bilirubin
Renal			Increased BUN, increased serum creatinine, increased urinary creatinine

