210 AEs assessed as probably related by primary SOC and preferred term: Safety Analysis Set

211 Related AEs by primary SOC and preferred term: Safety Analysis Set

212 Lesional/perilesional AEs by primary SOC and preferred term: Safety Analysis Set

213 Distant AEs by primary SOC and preferred term: Safety Analysis Set

214 AEs leading to withdrawal by primary SOC and preferred term: Safety Analysis Set

215 Haematology laboratory parameters from baseline (Visit 1) to Visit 4 (Week 4): Safety Analysis Set

216 Chemistry laboratory parameters from baseline to Visit 4 (Week 4): Safety Analysis Set

217 Haematology laboratory parameters categorised as low, normal or high at Visit 4 (Week 4) shown against baseline category: Safety Analysis Set

218 Chemistry laboratory parameters categorised as low, normal or high at Visit 4 (Week 4) shown against baseline category: Safety Analysis Set

Trial ID: LP0053-1422	Date: 21JUN2019	Version: 1.0 Page 23 of 26
------------------------------	------------------------	-------------------------------

219 Urinary parameters categorised as absent or present at Visit 4 (Week 4) shown against baseline category: Safety Analysis Set

Patient Data Listings (Appendix 1)

Listing 1.7.1 Randomisation code and treatment: Randomised subjects

Patient Data Listings (Appendix 2)

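### Urine glucose and protein are graded by the laboratory but summarised only as absent or present, so worsening from a positive baseline cannot show in the urine shift table

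*Protocol*

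**What the plan says.** Protocol section 8.6 lists "Urine Glucose, urine protein" under the heading "Urine, semi-quantitatively", with the samples analysed by the central laboratory. Neither document states how many grades the scale has.

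For the analysis, protocol section 11.3.8.2 says "Urine glucose and protein will be classified as" absent or present, and then: "Shift tables will be produced showing the categories at Visit 1 (baseline) against those at Visit 4 (end of Week 4"). The same section plans numerical summaries of observed values and change from baseline, but only for haematology and chemistry.

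SAP section 6.7.3 follows the protocol and adds only a rule for a missing Visit 1 value. SAP Appendix I lists one urine table, Table 219: "Urinary parameters categorised as absent or present at Visit 4 (Week 4) shown against" the baseline category. Individual results go to Listing 2.8.1 (all laboratory measurements) and Listing 2.8.3 (abnormal ones).

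**The concern.** The trial collects an ordered result and analyses a two-level one. A subject who moves from the lowest positive grade to the highest falls in the present/present cell, the same cell as a subject who did not change. A subject who goes from negative to the lowest positive grade (if that counts as present) falls in the same cell as one who goes from negative to the top grade.

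The measure has some relevance here. Protocol section 10.3 names, among effects seen with systemic steroid treatment that may also occur with topical use, "adrenocortical suppression or impact on the metabolic control of diabetes mellitus". It also links calcipotriol to a decline in kidney function associated with hypercalcaemia. Blood glucose is not in the section 8.6 panel, so urine glucose and HbA1c are the only glucose-related measures. The package insert in Appendix 2 reports "anaemia and glucose urine present in 2 patients each" in the Japanese ointment and gel studies.

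The secondary objective is to compare safety between the two products, and such a comparison is made from by-group summaries rather than from subject listings.

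**Working it through.** The plan gives no figure to reproduce. The check has three parts.

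**1. Can a subject enter with a positive urine result?** Yes. No criterion in section 7.3 names diabetes, urine glucose or urine protein. The only laboratory value named as an exclusion is albumin-corrected serum calcium (criterion 12). Renal insufficiency excludes only when severe, Grade 3 or above (criterion 13).

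**2. Which worsening moves can the two-level table show?** Suppose the laboratory reports k ordered grades. The documents do not give k, so 3 to 7 is assumed. With the cut at the lowest positive grade:

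- possible worsening moves: k(k−1)/2
- moves that change cell (absent to any positive grade): k−1
- moves that start from present and stay in present/present: (k−1)(k−2)/2

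| k (assumed) | Worsening moves | Change cell | Hidden in present/present |
|---|---|---|---|
| 3 | 3 | 2 | 1 |
| 4 | 6 | 3 | 3 |
| 5 | 10 | 4 | 6 |
| 6 | 15 | 5 | 10 |
| 7 | 21 | 6 | 15 |

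If the lowest positive grade is instead counted as absent, the moves hidden in present/present are 0, 1, 3, 6 and 10 for k = 3 to 7. One further move, from negative to the lowest positive grade, is then hidden in absent/absent. For every k and both cut points, the number of worsening moves from present that the table shows is 0. These are counts of possible moves, not of subjects or probabilities.

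**3. Does another planned summary fill the gap?**

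- *Haematology and chemistry.* Their low/normal/high shift tables have the same ceiling (high to high), but Tables 215 and 216 back them with observed values and change from baseline. Urine has no such backing.
- *HbA1c.* It is in the haematology panel (section 8.6), so it falls under Tables 215 and 217.
- *Adverse events.* Section 8.6 requires a laboratory abnormality to be recorded as an AE if the investigator judges it clinically significant. Section 9.3.6 requires the same for clinically significant worsening of any condition. Section 11.3.8.1 counts an event that began before treatment and then worsened in severity as treatment emergent. Such events would reach the by-group AE tables.
- *Listings.* Listings 2.8.1 and 2.8.3 hold individual results without a group summary.

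**Background rate.** In Appendix 2 the reaction counts are 5 + 2 + 2 + (8 × 1) = 17 in 445 patients (3.8%), across 3 + 8 = 11 reaction types. Glucose in urine accounts for 2/445 = 0.4%, joint second by count.

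**The case against.** The strongest reply is that nothing here is inconsistent. The protocol and SAP agree, and collapsing a screening test for a descriptive safety table is a legitimate choice. Worsening that matters clinically has its own route: the AE rules cover abnormal laboratory results and aggravation from baseline, and the AE tables show them by treatment group, severity and causality. HbA1c has both a numerical summary and a shift table. The Appendix 2 precedent was itself reported as an adverse drug reaction, so this type of result has reached AE data before. Its name denotes presence, and absent to present is a change that Table 219 does show.

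Most of that stands, and it sets the size of the point. What it does not answer is that the AE route depends on a judgement of clinical significance made in an open trial (section 6.4), whereas a centrally analysed grade does not depend on that judgement. A rise in grade that no investigator considers significant appears in no group summary.

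A reader might go further and infer that worsening is lost from the trial altogether, or that glucose control is left to a two-level urine table alone. The AE rules, the listings and the HbA1c summaries show otherwise. A reader might also infer that HbA1c is too slow to help over four weeks, or that diabetic subjects are the most likely to worsen. The documents contain nothing on either, so the point does not use them.

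**Conclusion.** The point holds as a minor limitation of descriptive safety reporting. In Table 219 a subject positive at Visit 1 cannot be shown as worse, whatever the number of grades and whichever of the two cut points checked is used, and no other planned table summarises urine grade. The effect is confined to increases in grade that were not recorded as AEs. The primary endpoint, its test and the analysis sets are unaffected.

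The number of subjects affected cannot be estimated. It is the number who are positive at baseline and also rise in grade by Visit 4, and the documents give neither rate. It would be tempting to treat every baseline-positive subject as uninformative, but such a subject can still be shown moving to absent. The 2 in 445 figure does not size the problem either: it pools ointment and gel studies, and nothing in it indicates a rise in grade among patients who were already positive.

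The conclusion assumes that the laboratory reports at least two positive grades, which is how the word semi-quantitative is read here. A related gap is that neither document says which grades count as present.

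**What to change.** Build Table 219 as a Visit 1 by Visit 4 shift table on the grades the central laboratory reports, separately for urine glucose and urine protein and by treatment group. Add the number of subjects whose grade rose by one, and by two or more. If the absent/present table is also kept, state in the SAP which grades count as present, including how the lowest positive grade is handled.

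The cost is a sentence or two in SAP section 6.7.3 and one revised table shell. Protocol section 11.3.10 already allows changes to the planned analysis to be described in the SAP. The measurements are already planned, so no new data or visits are needed. The downside is a larger and sparser table.

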### 11.3.9 Interim Analysis

No interim analyses are planned.

### 11.3.10 General Principles

All significance tests will be two-sided using the 5% significance level. All confidence intervals will be presented with 95% degree of confidence.

An observed cases approach will be used for tabulations of data by visit (i.e. involving only those subjects who attended each specific visit).

Categorical data will be summarised using the number and percentage of subjects in each category and treatment group. Continuous data will be summarised using the mean, median, standard deviation (SD), minimum and maximum values. For laboratory data, the geometric mean and coefficient of variation will be included.

‘Baseline’ value is defined as the value from the latest assessment before treatment, i.e. at Visit 1 (Day 1) before randomisation.

Any changes from the statistical analysis planned in this clinical trial protocol will be described and justified in a protocol amendment/the statistical analysis plan and/or in the clinical trial report dependent on the type of deviation.

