### 3.4 Ethical Consideration Statement

The purpose of this trial is to compare LEO 90100 foam and Dovobet® ointment in the treatment of psoriasis in Japanese subjects. The data obtained from this trial will contribute to the development of LEO 90100 foam, a therapy expected to be a useful treatment for psoriasis in the Japanese population.

Even though LEO 90100 foam is a different formulation of the approved product Dovobet® ointment, it contains the same active ingredients at the same concentration and is therefore expected to have a similar safety and efficacy profile. The results of the clinical trials

conducted with Dovobet® ointment in Japan were similar to the results of the clinical trials conducted overseas. Postmarketing surveillance has not revealed any signals indicating a difference between Japanese subjects and non-Japanese subjects.

Subjects participating in the trial will be under the careful supervision of an experienced dermatologist during the entire course of the trial.

Considering the above, this trial is assumed to involve a minimal risk to the participating subjects.

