## **5 Trial Endpoints**

### **5.1 Primary Endpoint**

The primary endpoint is 'overall improvement rate' for the target lesion at Visit 4 (end of Week 4), defined as 'substantial resolution' of clinical signs or at least 'moderately improved' in the general change in the target lesion. 'Substantial resolution' is defined as a clinical score for thickness and scaliness of 0 and a clinical score for redness of 1 or less in the severity of clinical signs of the target lesion.

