### Treatment period

The treatment period will last for up to 4 weeks. Trial visits will be performed on Day 1 (Visit 1) and after 1, 2 and 4 weeks (Visits 2, 3 and 4). Visit 2 and Visit 3 should be performed within  $\pm 1$  day of the scheduled time (Day 7-9 and Day 14-16, respectively), and Visit 4 should be performed within  $\pm 2$  days of the scheduled time (Day 27-31), in all cases relative to Visit 1. If they are outside this window, the (sub)investigator should record the reason in the patient's medical record.

At Visit 1, subjects will be randomised to receive treatment with either LEO 90100 foam or Dovobet® ointment. Trial medication will be applied once daily to psoriasis on a target lesion of the body. After this application on the target lesion, subjects will also apply trial medication to any other areas of psoriasis, excluding psoriasis on the scalp, face, genitals, and skin folds (axillae, groin, infra-mammary, those around the buttocks and the perianal area).

On the assessment day of the target lesion (Visit 1, Visit 2, Visit 3 and Visit 4), subject should not apply any topical treatment including emollients on the target lesion before the visit. Showering or bathing should also be avoided.

Subjects with the target lesion achieving 'substantial resolution', as defined in section 5, before the end of 4 weeks' treatment will complete the trial at this time (although they will still be required to attend the follow-up visit up to 14 days later, if applicable; see below).

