## 7.7 Withdrawal Criteria

Subjects **may** withdraw from the trial for any of the following reasons:

1. *Unacceptable treatment efficacy*: the (sub)investigator is free to withdraw the subject at any time based on a medical judgement.
2. *Unacceptable AEs*: any AE that the (sub)investigator or the subject considers unacceptable.
3. *Exclusion criteria*: any exclusion criteria which emerge/become apparent during the subject’s participation in the clinical trial.
4. *Voluntary withdrawal*: subjects are free to withdraw from the clinical trial at any time and for any reason.
5. *Other reasons*: other reasons than stated above which require the subject to (be) withdraw(n) should be specified.

Subjects **must** be withdrawn if they are found to have become pregnant.

Subjects with the target lesion achieving ‘substantial resolution’, as defined in section 5, before the end of 4 weeks’ treatment will complete the trial at this time (although will still be required to attend the follow-up visit up to 14 days later if applicable)

Subjects who are discovered, after randomisation, not to have fulfilled all inclusion/exclusion criteria at the time of randomisation, should be withdrawn from treatment unless the (sub)investigator finds withdrawal inappropriate, based on clinical and ethical evaluation.

Reason(s) for withdrawal will be recorded in the eCRF. Withdrawn subjects will not be substituted.

Completion of trial is defined as:

A subject who attends Visit 4 on Day 29 or later

or

A subject who attends Visit 4 earlier than Day 29, but the reason for attending earlier than Day 29 is not because (a) the (sub)investigator wishes to withdraw the subject, or (b) the subject wishes to withdraw

or

Subjects with the target lesion achieving ‘substantial resolution’, as defined in section 5, before the end of 4 weeks treatment.

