## 8 Trial Schedule and Assessments

### 8.1 Schedule of Trial Procedures

Visits	Screening	1	2	3	4/EoT	Unscheduled/early withdrawal	Follow up d
Days	-28 to -3 a	1	8	15	29		Up to +14
Visit Window e	-	-	+/- 1	+/- 1	+/- 2		-
Informed consent	x						
Demographics/baseline characteristics	x						
Medical history/concurrent diagnoses	x						
Concurrent procedures	x	x	x	x	x	x	x
Concurrent medication	x	x	x	x	x	x	x
Selection of a target lesion	x						
Laboratory assessment	x	x			x	x	
Adverse events	x	x	x	x	x	x	x
Physical examination	x	x	x	x	x	x	x
Pregnancy test b		x			x	x	
Inclusion/exclusion criteria check	x	x					
Randomisation		x					
Investigator's assessment – sign score of target lesion		x	x	x	x	x	
Investigator's assessment – general change in target lesion			x	x	x	x	
Subject's assessment: time spent for application f					x	x	
Subject's assessment: ease of application f					x	x	
Supply IMP		x	x	x			
Collect unused IMP			x	x	x	x	
Compliance check			x	x	x	x	
Completion of End of trial form	x c				x	x c	

a The minimum time between Screening Visit and Visit 1 is 3 days

b For females of child-bearing potential

c For screening failures and early withdrawals only

d Follow-up only if ongoing related AEs present at last on-treatment visit; to be done 14 days after this visit, or when final outcome established, whichever comes first

e Relative to Visit 1

f Compared to previous topical treatment

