#### General change in target lesion

At Visits 2-4, the general change in the target lesion from Visit 1 will be recorded according to the 5-point scale below.

Markedly improved	+++	A very definite improvement (approx. 75% or more)
Moderately improved	++	A definite improvement (approx. 50%)
Slightly improved	+	Some definite improvement (approx. 25%), however, significant signs remain
Unchanged	+/-	No change
Aggravated	-	Worsened

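### The Visit 3 overall improvement rate (Tables E3/E4) leaves out subjects who have already left, whether cleared or withdrawn, so it is not the rate in the FAS or PPAS

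*Protocol*

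**What the plan says.** **By-visit rule.** Protocol 11.3.10: "An observed cases approach will be used for tabulations of data by visit (i.e. involving only those subjects who attended each specific visit". SAP 6.8.2 likewise counts attendees, inside or outside the visit window.

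**Early exit for success.** Protocol 6.1 (Treatment period) says that subjects whose target lesion resolves substantially before the end of 4 weeks' "treatment will complete the trial at this time (although they will still be required to attend the follow-up visit" if one applies. Protocol 7.7 counts them as completers. Substantial resolution means "a clinical score for thickness and scaliness of 0 and a clinical score for redness of 1 or less" (Protocol 5.1) and by itself satisfies overall improvement.

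**Early exit for failure.** Under unacceptable efficacy, Protocol 7.7 says "the (sub)investigator is free to withdraw the subject at any time based on a medical judgement".

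**LOCF.** Protocol 11.3.11 names LOCF in general terms. SAP 6.6.1 to 6.6.3 and 6.8.1 apply it at Visit 4, to the primary endpoint, the total sign score and each sign. In SAP Appendix I, Tables E1, E2, E5, E6 and E9 to E11 are labelled LOCF; E3, E4, E12 and E13 are not.

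**Analysis sets.** Protocol 11.3.5 analyses the secondary endpoints on the FAS and PPAS, and Protocol 11.2 puts all randomised subjects in the FAS. E3 and E4 are titled FAS and PPAS.

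**The concern.** Overall improvement at Visits 2 and 3 is a named secondary endpoint. A reader who sees a Visit 3 percentage in a table titled FAS is likely to take it as the share of the FAS that had improved. Under the attendees-only rule it is the share among those still in the trial, and subjects leave for reasons tied to the outcome itself. The series across visits also changes basis: observed cases at Visits 2 and 3 (E3), then LOCF at Visit 4 (E1).

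The expectation in Protocol 11.3.11 of few or no dropouts does not settle this. Early resolvers are completers removed because treatment worked. If one arm clears lesions faster, it loses more responders from its Visit 3 rate and looks worse than it is.

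**Working it through.** **Inputs.** The documents give no rate for response, early resolution or withdrawal, so there is no by-visit figure of the plan's to reproduce. From Protocol 6.2 come N = 90 per arm and at least 80 completers, which allows for up to 90 − 80 = 10 non-completers. Everything else below is assumed.

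**Formula.** Let x be the responders at Visit 3 on the full denominator, r the subjects who left at Visit 2 with substantial resolution (all responders), and w the subjects withdrawn before Visit 3, taken as non-responders.

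- Full-set rate = x / N
- Printed rate = (x − r) / (N − r − w)
- The two are equal when w = r(N − x) / x

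**Visit 3 overall improvement, x = 63 (70.0%)**

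| r | w | Printed | Error (points) |
|---|---|---|---|
| 4 | 0 | 59/86 = 68.6% | −1.4 |
| 4 | 1 | 59/85 = 69.4% | −0.6 |
| 4 | 2 | 59/84 = 70.2% | +0.2 |
| 4 | 4 | 59/82 = 72.0% | +2.0 |
| 9 | 0 | 54/81 = 66.7% | −3.3 |
| 0 | 10 | 63/80 = 78.8% | +8.8 |

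For r = 4 the errors cancel at w = 4 × 27 / 63 = 1.7, so the sign changes between one and two withdrawals.

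**Range.** With full-set rates of 50% to 80% and no withdrawals, 2 to 18 resolvers lower the printed rate by between 0.5 points (70/88 = 79.5% against 80.0%) and 12.5 points (27/72 = 37.5% against 50.0%).

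**Between arms.** With equal true rates and no withdrawals:

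- at 70%, 4 against 1 resolvers print 59/86 = 68.6% and 62/89 = 69.7%, a difference of −1.1 points;
- at 60%, 9 against 2 print 45/81 = 55.6% and 52/88 = 59.1%, a difference of −3.5 points.

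Equal exits give a difference of 0.

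**E12 at Visit 3.** With 4 of 90 cleared at Visit 2 and 3 more at Visit 3, the Visit 3 column prints 3/86 = 3.5%. The cumulative share cleared is 7/90 = 7.8%.

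**E12 at Visit 4, two readings.** Suppose 20 more clear at Visit 4. If an early resolver's exit assessment stays under the visit attended, the column prints 20/83 = 24.1%. If it goes under Visit 4/EoT, the column prints 27/90 = 30.0%. The documents point both ways:

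- For Visit 4/EoT: that is the column heading in Protocol 8.1. Protocol 8.6, 8.8, 8.9 and 8.13 take an early completer's other assessments in place of those at Visit 4. The end-of-trial form in the unscheduled column is limited to screening failures and early withdrawals.
- For the visit attended: SAP 6.6.1 treats an early resolver's Visit 4 value as missing and carries the last result forward. Protocol 8.12 has no in-place-of rule for the lesion assessment.

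On either reading a Visit 2 resolver has no Visit 3 assessment.

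**The case against.** The rule is disclosed in both documents, and the tables print counts with percentages, so denominators can be recovered. The affected tables carry no test or interval. The primary endpoint has LOCF and four sensitivity analyses. The foam "is therefore expected to have a similar safety and efficacy profile" (Protocol 3.4), so exits may be alike in both arms. Much can also be rebuilt: the E12 Visit 2 count restores resolvers to E3, summed E12 counts give cumulative clearance, and Listings 2.3.1, 2.6.1 and 2.6.2 serve for E4. Protocol 11.3.1 and SAP 6.3 promise reasons for leaving, and Listing 2.5.3 gives the end-of-trial form.

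All of that stands, and it limits the weight of the point. It does not remove it, because rebuilding a secondary endpoint from other tables is no substitute for planning it. Tables 107 and 108 are titled as reasons for withdrawal, so it is not certain that early resolvers, who are completers, will appear there.

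A reader might infer that the SAP contradicts Protocol 11.3.11 by confining LOCF to Visit 4. The documents do not support that: Protocol 11.3.10 already assigns by-visit tables to observed cases, and the SAP follows it. A reader might also infer that the Visit 4 column of E12 is certain to omit early resolvers; the text is ambiguous there.

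**Conclusion.** As the plan is written, the Visit 3 percentage in E3 and E4 is a rate among attendees, not the FAS or PPAS rate, whenever anyone has left early. E12 at Visit 3 has the same fault, and the Visit 4 columns of E12 and E13 need clarifying.

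The size and direction cannot be taken from the documents. In the illustration, 4 resolvers and 0 to 4 withdrawals in 90 move a 70.0% rate to anywhere from 68.6% to 72.0%. This assumes that resolvers stay resolved and that withdrawals are non-responders.

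Two stronger conclusions are not supported. One is that the printed rate is always too low, since withdrawals push it up. The other is that the trial's main result is biased, since E1, E2, E5, E6 and E9 to E11 use LOCF. This is a cheap improvement to descriptive tables.

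**What to change.** Add to SAP 6.8.1/6.8.2, stated as an addition to Protocol 11.3.10:

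> For E3, E4 and E12, a second version will use all subjects in the analysis set as denominator. Missing later visits will be filled by LOCF for early resolvers and withdrawals alike. Subjects with no post-baseline assessment will count as not improved or not resolved. The observed-cases version will be shown beside it. Footnotes will give the number of early resolvers and of other withdrawals by arm and visit. An early resolver's exit assessment will be tabulated under [the visit attended / Visit 4/EoT; sponsor to choose].

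Both kinds of exit must be carried forward. With 4 resolvers and 2 withdrawals, carrying only the resolvers gives 63/88 = 71.6%, whereas carrying both gives 63/90 = 70.0%. The rule for subjects without a post-baseline assessment is needed because "At Visits 2-4, the general change in the target lesion from Visit 1 will be recorded according to the 5-point scale below" (Protocol 8.12), so they have no value to carry.

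No second version of E14 to E17 or E14_A to E17_A is needed. If 5% are resolvers with a change of −5.5 and the rest average −4.5, the mean moves only from 0.05 × (−5.5) + 0.95 × (−4.5) = −4.55 to −4.50. Most of these tables have LOCF counterparts at Visit 4.

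**Cost.** One SAP paragraph, a derivation flag, a second version of three tables, and footnotes. No new data: Protocol 8.1 already schedules the sign scores and the "general change in target lesion" at the unscheduled/early-withdrawal visit.

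**Downside.** The no-relapse assumption of SAP 6.6.1 and LOCF for withdrawals would reach a few more tables. Status after exit is not observed, and Protocol 10.3 warns: "There may be a risk of generalised pustular psoriasis or of rebound effects when discontinuing treatment". LOCF for withdrawals can mislead too: if 2 subjects carried as not improved would have responded, the table prints 63/90 = 70.0% where 65/90 = 72.2% is true. That is why observed cases stays alongside. If only one step is taken, the footnote counts would let a reader judge the Visit 3 rate.
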